### 8.2 Study Objectives

#### 8.2.1 Primary Objectives

- a. Phase 1: Determine the maximum tolerated dose of poly-ICLC that can be combined with pembrolizumab
- b. Phase II: Determine the response rate of metastatic MRP colon cancer that has progressed following two lines of therapy in the metastatic setting to the combination of pembrolizumab and poly-ICLC by RECIST 1.1.

#### 8.2.2 Secondary Objectives

- a. Phase I and II - Determine the adverse event profile and dose limiting toxicities of the combination of pembrolizumab and poly-ICLC
- b. Determine the progression free survival rate, overall survival rate and duration of response of recurrent metastatic MRP colon cancer to the combination of pembrolizumab and poly-ICLC

### 8.2.3 Exploratory Objectives

- a. Evaluation of inflammatory state in tumor biopsies with specific attention to definition of tumor infiltration with hematopoietic cells, cell surface signaling molecule expression.
- b. Evaluation of pre-treatment and post-treatment microarray panels in tumor samples and peripheral blood.

### 8.3 Study Design/Endpoints

Phase I: Classical 3+3 design will be employed and will include dose-escalation to determine the RP2D of Poly-ICLC to be combined with pembrolizumab. We will consider two dose levels, 1 and 2 mg of Poly-ICLC.

Phase II: Primary endpoint is the response rate defined according to RECIST 1.1 criteria. irRECIST response will be assessed as an exploratory endpoint.

### 8.4 Sample Size/Accrual Rate

For part 1: 3 to 12 patients will be used for the dose escalation part. The actual number of patients will depend on the DLT and MTD. We are expecting 3 patients per month to be enrolled in the study.

For Part 2: With the assumption that the RR rate for pembrolizumab alone is about  $H_0=5\%$ , 27 patients are needed to detect an increase in RR to  $H_1=20\%$  for the treatment combination to achieve 80% power and keep the probability of type I error ( $\alpha$ ) at 0.05. We are expecting accrual rate of 5 patients per month during the phase II portion of the study.

### 8.5 Analysis of Endpoints

#### 8.5.1 Analysis of Primary Endpoints

- a. A minimum of 3 patients will be treated depending on DLT. Dose level 1 (1mg) will be administered to a cohort of 3 patients. If 0 out of 3 experience DLT, then dose escalation will proceed to the dose level 2 (2mg). If one out of three patients experience DLT, a cohort of additional three patients will be assigned to the same dose level (1mg). If two or more patients of three (or six) patients experience DLT at the first dose level, the trial, then enrollment of patients will be stopped. If a maximum one patient experience DLT at dose level 2, then the dose will be declared the RP2D. If 2 or more out of 6 patients experience DLT at the second dose level, then the first dose level (1mg) will be declared the RD2D. The RP2D should have at least 6 patients enrolled at the dose level with a maximum of 1 patient experiencing DLT.
- b. To assess preliminary evidence of antitumor activity, in terms of Objective Response Rate (ORR). ORR will be calculated as the number of participants with complete response (CR) or partial response (PR) by RECIST criteria, divided by the total number of participant in the dataset. The ORR will be estimated for every estimated and the associated exact 95% CI will be provided.

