##### 3.1.2 Hypotheses:

- a. Poly-ICLC will generate an inflammatory response increasing epitope recognition and development of tumor reactive T cells at the tumor site. However, interferon alpha and gamma produced by the poly-ICLC will increase PD-L1 expression and limit new T cell development. Thus, PD1 blockade will increase the effectiveness of the therapy.
- b. Phase 1 – Combination of Poly-ICLC and Pembrolizumab is tolerable at the doses proposed for this intervention
- c. Phase 2 – Combination of poly-ICLC and pembrolizumab has increased efficacy compared to pembrolizumab alone in patients with colon cancer. The RR will increase to 20% for the combination treatment from an expected 5% response rate for pembrolizumab alone.

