## 8 STATISTICAL ANALYSIS PLAN

### 8.1 Introduction

This study has two parts:

- a. Phase I dose-escalation to determine the recommended phase II dose of Poly-ICLC to be combined with the standard dose of pembrolizumab. Patients with any solid tumor that is unresponsive to at least two lines of therapy is eligible for the dose escalation phase unless curative options exist.
- b. The combination will then be administered at the recommended phase II dose to in up to 27 patients with relapsed metastatic colon cancer. MSI-high patients will be excluded.

Descriptive statistics will be presented for primary and secondary endpoints. Summary statistics for continuous variables will include the mean, standard deviation, median, and range (minimum/maximum). Categorical variables will be presented as frequency counts and percentages; and time-to-event variables will be summarized by Kaplan-Meier medians and survival plots. Data listings will be created to support each table and to present all data. The data will be tabulated and analyzed with respect to patient enrollment and disposition, demographic and baseline characteristics, for primary efficacy and safety measures per study part (Phase I, II), and on a per dose level for phase I part. The primary efficacy analysis will be conducted on the efficacy evaluable population and safety analysis will be performed on the safety evaluable population. Maximum tolerated dose for of Poly-ICLC to be combined with pembrolizumab will be estimated based on the data from the 3+3 dose escalation. RP2D will then be determined based on the estimated MTD, which should not exceed 1/6 of RLT. SAS 9.3 software, or higher will be used for data analysis.

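### If the exact 95% CI planned for the ORR is the usual equal-tailed interval and is used to compare with 5%, 27 patients give about 65% power, not the stated 80%

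*Combined protocol and SAP*

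**What the plan says.** Section 3.1.2 gives the Phase 2 hypothesis: "The RR will increase to 20% for the combination treatment from an expected 5% response rate for pembrolizumab alone". Section 8.4 turns this into a sample size. With a null rate of 5%, "27 patients are needed to detect an increase in RR to" 20% "for the treatment combination to achieve 80% power and keep the probability of type I error" at 0.05. It names no test, no sidedness and no number of responses that would count as success.

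Section 8.5.1(b) defines the ORR as complete plus partial responses "divided by the total number of participant in the dataset", and adds that "the associated exact 95% CI will be provided". It does not name the interval method, and it does not say how the interval is to be set against 5%. Section 8.1 describes the approach in general terms: "Descriptive statistics will be presented for primary and secondary endpoints". Section 8.7 rules out an interim analysis, so no stopping boundary supplies a cut-off either.

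**The concern.** Phase 2 is sized as a comparison with 5%, with a stated error rate and power. The only quantity planned for the primary endpoint that could carry that comparison is the 95% interval. In its usual form, that interval leaves 2.5% in each tail, whereas the sample size fits a rule that spends the full 5% in the upper tail.

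The two rules part at exactly 4 responses. There the sizing rule would call the trial positive, while the usual interval would still contain 5%. The plan does not say which governs, so in an open-label, historically controlled trial the choice could be made after the response count is known. A reader who judges the result by the interval would also be relying on a power figure that does not belong to it.

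**Working it through.** **Inputs.** Null rate 5% and target rate 20% (sections 3.1.2 and 8.4); n = 27, power 80%, alpha 0.05 (8.4); exact 95% CI (8.5.1(b)); single stage (8.7). Assumptions: all 27 patients are in the denominator, and exact means Clopper-Pearson unless stated otherwise.

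**Step 1: reproduce the 27.** Let X be the number of responders, binomial with n = 27. A rule of success at r or more has size P(X ≥ r | 0.05) and power P(X ≥ r | 0.20).

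| Success at | Size at 5% | Power at 20% |
|---|---|---|
| 3 or more | 0.150 | 0.928 |
| 4 or more | 0.0437 | 0.8177 |
| 5 or more | 0.0100 | 0.6520 |

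The 4-or-more rule meets both targets. With 26 patients the same rule has power 0.793, so 27 is the smallest exact one-sided 0.05 design with at least 80% power. The plan's figure reproduces.

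**Step 2: other routes to about 27.**
- The two-sided normal approximation is n = (1.960 × √(0.05 × 0.95) + 0.842 × √(0.20 × 0.80))² / 0.15² = 25.9, so 26. With 1.645 in place of 1.960 it gives 21.5, so 22.
- The two-sided exact test by the minimum-likelihood method also rejects at 4/27. Its p-value adds a lower-tail outcome only if that outcome is no more probable than X = 4. Under 5%, P(X = 4) = 0.0437 − 0.0100 = 0.0337, whereas P(X = 0) = 0.95²⁷ = 0.250. Nothing is added, so p = 0.0437 and the power is again 0.818.

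**Step 3: the equal-tailed 95% interval.** The Clopper-Pearson lower limit is the p that solves P(X ≥ x | p) = 0.025. It lies above 5% only if P(X ≥ x | 0.05) is below 0.025. From Step 1 the tail is 0.0437 at x = 4 (5% not excluded) and 0.0100 at x = 5 (5% excluded). The limits agree:

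| Responses | 95% CI | 90% CI |
|---|---|---|
| 3/27 | 2.35% to 29.2% | 3.10% to 26.3% |
| 4/27 | 4.19% to 33.7% | 5.22% to 30.8% |
| 5/27 | 6.30% to 38.1% | 7.59% to 35.1% |

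If success means that this 95% interval excludes 5%, 5/27 is needed, with power 0.652 and upper-tail size 0.010. The 90% interval first excludes 5% at 4/27, the same cut-off as the sizing.

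**Step 4: size of the gap.** P(X = 4 | 0.20) = 0.8177 − 0.6520 = 0.166, so about 17 points of power. That is 0.166 / 0.818 = 20% of the outcomes that the sizing rule would call positive.

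**Step 5: dependence on the method.** The Blaker interval is also exact, but not equal-tailed. At 4/27 its 95% limits are about 5.2% and 32.8%, which exclude 5%. Under that method the cut-off stays at 4 and the power at 0.818.

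**The case against.** The strongest reply is that an interval has no power until it is paired with a decision rule, and the plan contains none. Section 8.5.1(b) only promises to report the interval, under an aim of looking for preliminary activity. Section 8.1 calls the presentation descriptive, and section 8.5.2 attaches 95% intervals to the secondary time-to-event endpoints as well. On this view the 95% CI is routine reporting and takes nothing from section 8.4. The reply also notes that the plan names no interval method, and that another exact method removes the discrepancy.

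Both points stand, and they limit the claim. A reader might infer that sections 8.4 and 8.5.1 contradict each other, or that the trial simply has 65% power. The documents do not support either, because they never make exclusion of 5% by the 95% CI the success criterion. A reader might also infer that the 80% power can be obtained only from a one-sided test. Step 2 shows otherwise: the discrepancy belongs to intervals with 2.5% in each tail, not to two-sided testing as such.

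The reply does not remove the gap. If the interval is purely descriptive, the alpha and power in 8.4 attach to no planned analysis. If it is used for the comparison, the conclusion at 4/27 turns on a method that the plan does not name.

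**Conclusion.** The point holds conditionally. If the interval in 8.5.1(b) is Clopper-Pearson and is used to compare with 5%, success needs 5/27 rather than 4/27. Power at a true rate of 20% is then about 65% instead of the stated 80%, with size 0.010 instead of 0.044. The effect is confined to exactly 4 responses; with 3 or fewer, or 5 or more, the two rules agree.

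Clopper-Pearson is the usual meaning of an exact 95% CI for a proportion, but it is an assumption here, as is the use of the interval as the criterion. The figures also assume 27 patients in the denominator. Section 8.6 defines a treated-patient set, section 8.1 an efficacy evaluable one, and section 5.10 allows replacement, so the final number could differ.

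It would be wrong to read this as an error in the sample size: 27 is right for the exact one-sided design.

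**What to change.** In section 8.5.1(b), state that the ORR is compared with 5% by an exact one-sided binomial test at 0.05, with success at 4 or more responses among 27. Report it with the matching Clopper-Pearson 90% two-sided CI or one-sided 95% lower limit (5.2% at 4/27). Name the 95% CI as Clopper-Pearson and descriptive. Section 8.4 should cite the same test, with size 0.044 and power 0.818.

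Alternatively, make the Clopper-Pearson 95% CI the criterion and restate the power in section 8.4 as about 65%.

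Under the first option, define the cut-off through the test, so that it follows the number analysed. It stays at 4 for 28 patients (size 0.049) but becomes 5 for 29 (size 0.014, power 0.716).

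The cost is a sentence or two in the SAP, settled before the response count is analysed. No patients need to be added. The alternative costs a less favourable power statement.

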#### 8.5.2 Analysis of Secondary Endpoints

- a. The adverse event profile will be presented by dose level of the combination treatment for the phase I portion.
- b. The progression free survival rate, overall survival rate and duration of response of recurrent metastatic MRP colon cancer to the combination of pembrolizumab and poly-ICLC administered at RP2D will be estimated along with the correspondent 95%

confidence interval. In addition, the 20-week PFS rate along with its 95% CI will be estimated and presented.

## 8.6 Analysis Datasets

Analysis will be conducted on the modified intent-to-treat set (mITT), which includes all enrolled subjects treated with at least 1 dose (or partial dose) of the study medications. The mITT set will be used for all safety and preliminary efficacy analysis.

## 8.7 Interim Analysis

No interim analysis is applicable for the proposed study.

# 9 LABELING, PACKAGING, STORAGE AND RETURN OF CLINICAL SUPPLIES

**Table 8. Product Descriptions**

Product Name & Potency	Dosage Form
Poly-ICLC 2mg/vial	Suspension for injection (IM)
Pembrolizumab 100 mg/ 4mL	Solution for injection (IV)

## 9.1 Investigational Products

The investigator shall take responsibility for and shall take all steps to maintain appropriate records and ensure appropriate supply, storage, handling, distribution and usage of investigational product in accordance with the protocol and any applicable laws and regulations.

The use of both pembrolizumab and poly-ICLC are considered investigational in this clinical trial, which is conducted under IND#129974, held by [name].

### 9.1.1 Pembrolizumab (MK-3475, Keytruda®)

Pembrolizumab will be provided by Merck for use in this investigational setting. Pembrolizumab is provided as a white to off white lyophilized powder (50 mg/vial) or as a liquid solution (100 mg/vial) in Type I glass vials intended for single use only. Pembrolizumab Powder for Solution for Infusion, 50 mg/vial, is reconstituted with sterile water for injection prior to use. The drug product is stored as a stable lyophilized powder or liquid solution under refrigerated conditions (2 to 8°C).

The lyophilized drug product after reconstitution with sterile water for injection, and the liquid drug product are a clear to opalescent solutions, essentially free of visible particles. The reconstituted lyophilized product and the liquid product are intended for IV administration. The reconstituted drug product solution or the liquid drug product can be further diluted with normal saline or 5% dextrose in the concentration range of 1 to 10 mg/mL in intravenous (IV) containers made of polyvinyl chloride (PVC) or non-PVC material. Reconstituted vials should be immediately used to prepare the infusion solution in the IV bag and the infusion solution should be immediately administered. Diluted pembrolizumab solutions may be stored at room temperature for a cumulative time of up to 4 hours. This includes room temperature storage of admixture solutions in the IV bags and the duration of infusion. In addition, IV bags can be stored at 2 to 8°C for up to a cumulative time of 20 hours. This recommendation is based on up to 24 hours of room temperature and up to 24 hours of refrigerated stability data of diluted MK-

3475 solutions in the IV bags. For each individual trial, clinical supplies are to be stored in accordance with specific instructions on the label.

### 9.1.2 POLY-ICLC (Hiltonol®)

Poly-ICLC is classified as an investigational new drug. It is a synthetic complex of polyinosinic and polycytidylic acid, stabilized with polylysine and carboxymethyl cellulose.

#### How supplied

Poly-ICLC is supplied by the manufacturer (Oncovir) in vials containing 1.8mg/mL opalescent solution. Drug supply for “at home” study drug administrations will follow local investigational pharmacy procedures.

Each vial poly-ICLC supplied by the manufacturer will be labeled with the following information:

Drug Name  
Concentration  
Storage Conditions  
Lot Number  
Date of Manufacture, Manufacturer  
Investigational Use Statement

#### Storage and stability

Poly-ICLC is stable at room temperature for at least 4 weeks. Treatment sites are asked to store the drug at approximately 2-8 °C. Study subjects will have Poly-ICLC administered at home, and will be advised to store their doses in a standard refrigerator. The vials should not be frozen.

#### Supplier

The drug to be used in this study is prepared and packaged using GMP conditions, under contract to Oncovir, Inc. It is then tested for quality, activity, sterility and pyrogenicity before release to the site pharmacy for clinical use.

## 9.2 Packaging and Labeling Information

Clinical supplies will be affixed with a clinical label in accordance with regulatory requirements.

## 9.3 Clinical Supplies Disclosure

This trial is open-label; therefore, the subject, the trial site personnel, the Sponsor and/or designee are not blinded to treatment. Drug identity (name, strength) is included in the label text; random code/disclosure envelopes or lists are not provided.

#### **9.4 Storage and Handling Requirements**

Clinical supplies must be stored in a secure, limited-access location under the storage conditions specified on the label.

Receipt and dispensing of trial medication must be recorded by an authorized person at the trial site.

Clinical supplies may not be used for any purpose other than that stated in the protocol.

#### **9.5 Returns and Reconciliation**

The investigator is responsible for keeping accurate records of the clinical supplies received from Merck or designee, the amount dispensed to and returned by the subjects and the amount remaining at the conclusion of the trial.

Upon completion or termination of the study, all unused and/or partially used pembrolizumab will be destroyed at the site per institutional policy. All unused and/or partially used poly-ICLC will be returned to Oncovir for destruction. It is the Investigator's responsibility to arrange for disposal of all empty containers, provided that procedures for proper disposal have been established according to applicable federal, state, local and institutional guidelines and procedures, and provided that appropriate records of disposal are kept.

### **10 ADMINISTRATIVE AND REGULATORY DETAILS**

#### **10.1 Confidentiality**

Only the investigator, the members of the research team, the sponsor, authorized officials from state and federal governments such as the Food and Drug Administration (FDA) or the Office of Human Research Protections (OHRP), and authorized representatives of the Western Institutional Review Board (WIRB) and Augusta University will have access to confidential data which would identify participants, unless specifically required to be disclosed by state or federal law. Because of the need to release information to these parties, absolute confidentiality cannot be guaranteed. The results of this study may be presented at meetings or in publications. However, participants will not be identified in any reports or publications resulting from the study. All reasonable steps will be taken to ensure confidentiality.

#### **10.2 Compliance with Financial Disclosure Requirements**

Investigators participating in the study will comply with federal and Augusta University financial disclosure requirements.

#### **10.3 Compliance with Law, Audit and Debarment**

Investigators will comply with federal and state laws. This study will be audited by the Georgia Cancer Center's auditing team. Investigators who have been debarred from clinical trial participation by the FDA may not participate in this trial.

#### **10.4 Compliance with Trial Registration and Results Posting Requirements**

Under the terms of the Food and Drug Administration Modernization Act (FDAMA) and the Food and Drug Administration Amendments Act (FDAAA), the Sponsor of the trial is solely responsible for determining whether the trial and its results are subject to the requirements for submission to the Clinical Trials Data Bank, <http://www.clinicaltrials.gov>. Information posted will allow subjects to identify potentially appropriate trials for their disease conditions and pursue participation by calling a central contact number for further information on appropriate trial locations and trial site contact information.

## 10.5 Quality Management System

### 10.6 Data Management

The DM (Data Monitor) Console is OnCore's data management tool and is the validation and management workspace for online forms in OnCore.

Electronic case report forms (eCRFs) are created in the eCRFs Console, and attached to specific protocol calendar visits for completion by the coordinator.

#### 10.6.1 Data Entry

##### Recording and handling data

In OnCore, when a subject visit as occurred, forms that need to be completed are listed on the Forms by Status > To Do Forms tab. Data is recorded specific to each form/visit. By opening the form, it becomes "Active," and the coordinator can continue to work on the form until the "Complete" button is selected. In declaring a form as complete, coordinators are in effect stating that the form is completely filled-out and is ready for a data monitor (DM) to validate the data.

##### Subject documents (questionnaires, diaries)

Subject documents, such as questionnaires and diaries, completed by the subject on paper, is then manually transcribed and entered into OnCore by the research staff.

#### 10.6.2 Query Management

In the DM Console, forms are categorized by the following statuses:

##### To Do

Assigned to forms for a subject visit marked as Occurred. This status will remain until form data entry begins.

##### Started

Assigned to a form when the data entry process is started. This status is set the first time the form is accessed.

##### Completed

Assigned when the form is declared as Completed.

##### Queried

Assigned when the Data Monitor adds a note questioning the form data. The CRA is expected to respond.

##### Amended

Assigned when the CRA responds to a Queried form. The response is sent to the Data Monitor.

##### Missed

Assigned to a form that has been marked as Missed or occurs on a visit or procedure that was marked as Missed.

### **Additional**

Assigned to an additional form instance created for a subject's visit.

### **Validated**

Assigned when a Data Monitor declares the form data is valid. Validated forms are not editable.

### **Locked**

Assigned when a Data Monitor locks the form, declaring the form data as unchangeable. A special security privilege is required to undo this status.

